7.1.6. Adverse Events

The accepted regulatory definition for an adverse event is provided in [Section 11.1](#). The occurrence of adverse events from the time the ICF is signed until the first dose should be recorded under medical history in the eCRF form. All medical occurrences after the first dose with study drug until 30 days after the last dose of study drug that meet the adverse event definition must be recorded as AEs in the eCRF. Laboratory abnormalities designated clinically significant by the Investigator will also be documented as adverse events. Additional important requirements for adverse event and serious adverse event reporting are explained in [Section 11.2.2](#).

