7.6.4. T/B/NK Cell Count

The blood sample(s) for T/B/NK cell count ($CD3^+$, $CD4^+$, $CD8^+$, $CD19^+$, $CD16/56^+$) must be collected predose at the time points specified in the Schedule of Assessments ([Appendix 1](#)).

These samples will be sent to a central laboratory for testing.

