10.6.2. Clinical Laboratory Tests

Laboratory tests will be summarized separately for hematology and serum chemistry. Local laboratory results will be converted based on the normal ranges and standardized using the SI unit. Selected hematologic and chemistry laboratory parameters are detailed in [Section 7.5](#). Descriptive statistics will be provided for the values of selected clinical laboratory tests at each scheduled on-treatment evaluation including the final value. Percent change from baseline to each scheduled on-treatment evaluation and to the final value will also be summarized. For selected variables, the mean value and mean percent change over time will be presented graphically.

A summary of the shifts in selected laboratory hematology and serum chemistry parameters from baseline to the worst toxicity grade during the study will be provided. The worst toxicity grade during the study will be tabulated.

All laboratory values will be converted to standard international units and will be graded using the [NCI CTCAE Version 4.03](#). Standard methods for summarizing laboratory variables will be used, including the use of summary statistics and shift tables.

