1 INTRODUCTION

This statistical analysis plan (SAP) is based on Protocol Amendment 5, dated on 01JUN2016, and is to define key elements including variable definitions, and statistical methods for analysis of data in the evaluation of efficacy and safety of the study PCYC-1123-CA. Analyses of biomarker and pharmacokinetics data will be addressed in separate documents.

Analysis methods specified in this document take precedence over those described in the protocol, should there be any difference.

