5 SAFETY EVALUATION

Safety data for the all-treated population will be summarized for Phase 1b by the dose for Phase 2, unless otherwise indicated. Table 5 summarizes the safety analyses to be conducted.

Adverse events will be coded in accordance with the Medical Dictionary for Regulatory Activities (MedDRA). Severity of AEs will be graded by the investigator according the NCI Common Terminology Criteria for Adverse Events (NCI-CTCAE) (version 22.1 or higher).

Statistical Analysis Plan

PCYC-1123-CA

20APR2020

In general, the treatment-emergent period is defined as the period from the date of the first dose of study treatment up to 30 days after the date of the last dose of study treatment or the day before initiation of subsequent anticancer therapy, whichever comes first. Treatment-emergent AEs are those events that occur or worsen during the treatment-emergent period or that are related to the study treatment or events with a complete missing onset date but with a resolution date during the treatment phase.

All laboratory values will be converted to and reported as international standard (SI) units. In general, only data from the central laboratory will be summarized and analyzed. Laboratory parameters will be graded using the NCI CTCAE (version 4.03 or higher). Unless otherwise specified, only baseline and post-baseline values collected during the treatment-emergent period will be included in the safety analysis.

Table 5: Summary of Safety Assessments

Assessment Type	Definition	Analysis Methods
AE	TEAEs, SAEs, grade 3 or higher TEAEs, study treatment-related TEAEs, TEAEs as the primary reason for treatment discontinuation, TEAEs leading to treatment discontinuation, TEAEs leading to dose reduction, TEAEs leading to death, protocol-defined events of special interest and other safety observations	Descriptive summary statistics and/or listings
Lab	Worst post-baseline toxicity grade for selected CTCAE gradable hematology and chemistry. Abnormalities in creatinine clearance, uric acid, and liver function.	Descriptive summary statistics and/or listings. For gradable lab results, the worst toxicity grade during the study will be tabulated and the summary of treatment-emergent abnormal laboratory results with 2 or more grade worsening will be provided.
Vital Signs and other Observations Related to Safety	SBP, DBP, heart rate, body temperature, weight, and ECOG PS	The baseline and the change from baseline will be summarized by scheduled visits.

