6 CHANGES IN PROTOCOL PLANNED ANALYSIS

Per protocol, an analysis will occur approximately 12 months after the last subject initiates study treatment or when all subjects have discontinued from the study treatment, whichever occurs first, and will be reported in the Clinical Study Report (CSR). Since the study results were summarized and presented at the American Society of Hematology Annual Meeting 2019, which was close to the time for that planned analysis, a decision was made to delay the clinical study report, which will be prepared at the final follow-up analysis, which will occur 24 months or 2 years after the last subject has been enrolled.

Statistical Analysis Plan

PCYC-1123-CA

20APR2020

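### The SAP limits laboratory summaries to central-laboratory data, but the protocol plans hematology and chemistry from local results, and the change is not declared

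*SAP*

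**What the plan says.** SAP section 5 states, in its paragraph on laboratory values: "In general, only data from the central laboratory will be summarized and analyzed". No exception is named. Table 5 in the same section then promises "Worst post-baseline toxicity grade for selected CTCAE gradable hematology and chemistry", a summary of abnormalities that worsen by two or more grades, and abnormalities in creatinine clearance, uric acid and liver function.

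Protocol 10.6.2 sets its scope with "Laboratory tests will be summarized separately for hematology and serum chemistry" and continues: "Local laboratory results will be converted based on the normal ranges and standardized using the SI unit". It does not mention central-laboratory data.

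SAP section 1 settles conflicts in its own favour: "Analysis methods specified in this document take precedence over those described in the protocol, should there be any difference". SAP section 6, which lists changes from the protocol's planned analysis, covers only the timing of reporting ("a decision was made to delay the clinical study report"). It says nothing about the source of laboratory data.

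**The concern.** The two documents give different sources for the same tables, and the one that governs names the source the protocol does not appear to provide for. If the SAP sentence is applied as written, local hematology and chemistry results drop out and the laboratory part of Table 5 has no identified data behind it. If it is not applied, the programmer chooses the source with no SAP rule to support the choice.

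The adverse event tables do not fill the gap. Protocol 7.1.6 says: "Laboratory abnormalities designated clinically significant by the Investigator will also be documented as adverse events". An abnormal value that the investigator does not so designate appears only in laboratory tables graded from the values themselves. This matters here because protocol 1.14.2 expects neutropenia with each of the three study drugs, and worst-grade tables built from measured counts are the systematic record of it.

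**Working it through.** The plan gives no figure to reproduce. The check compares the passages and then counts the scheduled samples that the rule could affect.

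**Where the protocol assigns central testing**

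| Sample | Protocol section | Laboratory named | In SAP Table 5 laboratory row? |
|---|---|---|---|
| Biomarker blood | 7.6.2 | Central | No |
| IHC subtype | 7.6.3 | Central | No |
| T/B/NK counts | 7.6.4 | Central ("These samples will be sent to a central laboratory for testing") | No; exploratory, Table 4 |
| Serum immunoglobulins | 7.6.5 | Central | No; exploratory, Table 4 |
| Optional biopsies | 7.6.6 | Central | No |
| Hematology | 7.5.1 | None named | Yes |
| Serum chemistry, including uric acid and liver tests | 7.5.2 | None named | Yes |
| Creatinine clearance | 7.5.3 | None named | Yes |

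Table 5 has five laboratory items: hematology grade, chemistry grade, creatinine clearance, uric acid and liver function. Central testing is named in the protocol for 0 of the 5.

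**Is local testing a fair inference?** Protocol 10.6.2 refers to local results for these panels. Protocol 8.3 allows safety laboratory results from the 48 hours before Day 1 to be used for dosing. Protocol 5.5.5 makes the start of a cycle depend on Day 1 neutrophil and platelet counts. Protocol 12.7 has investigators keep laboratory normal values on file. All of this fits site testing but does not prove it. The Laboratory Manual, which might settle the point, is not available.

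**Scheduled hematology and chemistry sets per subject (protocol 8.2.1 to 8.3.13)**

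- Screening: 1
- Cycle 1, Days 1, 8, 15 and 22: 4
- Cycle 2, Days 1 and 15: 2
- Cycle 3, Days 1 and 15: 2
- Cycles 4, 5 and 6, Day 1: 3

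Total: 1 + 4 + 2 + 2 + 3 = 12. Screening and the pre-dose Cycle 1 Day 1 sample are baseline, so 12 − 2 = 10 are post-baseline.

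Creatinine clearance is scheduled less often: Screening and Day 1 of Cycles 1 to 6, so 1 + 6 = 7, of which 7 − 2 = 5 are post-baseline.

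**Range of effect.** Let *p* be the share of these results tested locally, which the documents do not give. The literal rule excludes 10 × *p* scheduled post-baseline sets for a subject still on treatment at Cycle 6 Day 1: 0 sets at *p* = 0% and all 10 at *p* = 100%.

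**The case against.** The strongest reply is that the sentence is qualified. It speaks of what is done *in general*, so local hematology and chemistry could be an unstated exception, with protocol 10.6.2 supplying the rule for them. The SAP sentence just before it, on conversion to SI units, is not limited to central data. Protocol 10.6.2 itself says how local results are standardized; it does not say that only local results are used. No available document says where these panels were run. If no central values existed, an empty laboratory table would be noticed at once. The outputs are also descriptive, with no formal safety testing planned.

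Much of this is fair, and it limits the claim. Local testing is an inference, and the size of the effect cannot be fixed. The five Table 5 items also overlap: uric acid and the liver tests belong to the chemistry panel, and Cockcroft-Gault clearance is calculated from serum creatinine. In substance, two panels are at stake.

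It does not remove the conflict. No exception is written. If the exception is the whole laboratory row of Table 5, the general rule governs nothing in that row. The precedence clause makes the central-only sentence the operative one. That an empty table would be noticed only means the source would be decided after the fact, in departure from the approved text.

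**Conclusion.** The concern holds. As written, the SAP rule conflicts with protocol 10.6.2, is not declared in SAP section 6, and excludes the apparent source of the Table 5 laboratory outputs. The textual mismatch is certain. The consequence rests on the inference that hematology and chemistry were tested mainly or only at local laboratories. On that assumption the exclusion reaches 10 post-baseline hematology and chemistry sets per subject through Cycle 6 Day 1 (5 for creatinine clearance). If all testing was central, nothing is lost, but the departure from 10.6.2 is still undeclared.

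The scope is limited to laboratory-value summaries. The response and survival endpoints, the investigator-graded adverse event tables and the DLT listing do not depend on it. The sponsor should correct it before the laboratory tables are produced.

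**What to change.** If these panels were tested locally, replace the central-only sentence in SAP section 5 with text such as:

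> Hematology, serum chemistry and creatinine clearance summaries use local laboratory results, converted to SI units and graded by CTCAE v4.03 as in protocol 10.6.2; T/B/NK counts and serum immunoglobulins use central laboratory results.

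The sponsor should first confirm the source against the Laboratory Manual. If any hematology or chemistry was tested centrally, state the source for each panel, say which result is used when both exist, and list the departure from 10.6.2 in SAP section 6.

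A separate clerical point in the same section: adverse events are graded by CTCAE version 22.1 or higher, while the SAP grades laboratory values by version 4.03 or higher and the protocol (10.6.1, 10.6.2 and 11.1.4) uses 4.03 throughout. Change the adverse event reference to 4.03.

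The cost is one or two SAP sentences and, if needed, one line in section 6. No new data are required.

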6 CHANGES IN PROTOCOL PLANNED ANALYSIS

Per protocol, an analysis will occur approximately 12 months after the last subject initiates study treatment or when all subjects have discontinued from the study treatment, whichever occurs first, and will be reported in the Clinical Study Report (CSR). Since the study results were summarized and presented at the American Society of Hematology Annual Meeting 2019, which was close to the time for that planned analysis, a decision was made to delay the clinical study report, which will be prepared at the final follow-up analysis, which will occur 24 months or 2 years after the last subject has been enrolled.

Statistical Analysis Plan

PCYC-1123-CA

20APR2020

